1.2 SCHEMA

Figure 1 - Graphical study design

1.3 SCHEDULE OF ACTIVITIES (SOA)

Table 1 - Schedule of assessments

Study Period/ Procedure	Screening	Primary analysis treatment period								Open-label extension treatment period				FU Period	Notes
Day or Week	Up to 60 d before D1	W1/D1	W12 (±7d)	W26 (±7d)	W39 (±7d)	W52 (±7d)	W65 (±7d)	W78 (±7d)	W104 (±7d)/EW ^a	W130 (±14d)	W156 (±14d)	W182 (±14d)	W208 (±14d)/EOT/EW ^b	W214 (±7d) SFU after EOT	
Visit number	1	2	3	4	4.1 ^c	5	5.1 ^c	6	7	8	9	10	11	12	
Visit at clinical site	X	X	X	X		X		X	X	X	X	X	X	X	For participants in United States, Visit 3, 8, 10 and 12 can be provided remotely under a decentralized clinical trial (DCT) model (Optional). For Visits 8 (W130), 10 (W182) and 12 (W214), may be provided remotely under a DCT model (optional) where applicable, allowed by local regulations, and approved by the participant.
Informed consent	X														
Inclusion/exclusion criteria	X	X													
Demographics and baseline characteristics	X														
Medical/surgical/treatment history/alcohol use history	X														
Experience of participating in the Natural History Study (NIH/NTSAD)	X														For participants in the United States only.

Study Period/ Procedure	Screening	Primary analysis treatment period								Open-label extension treatment period				FU Period	Notes
Day or Week	Up to 60 d before D1	W1/D1	W12 (±7d)	W26 (±7d)	W39 (±7d)	W52 (±7d)	W65 (±7d)	W78 (±7d)	W104 (±7d)/EW ^a	W130 (±14d)	W156 (±14d)	W182 (±14d)	W208 (±14d)/EOT/EW ^b	W214 (±7d) SFU after EOT	
Visit number	1	2	3	4	4.1 ^c	5	5.1 ^c	6	7	8	9	10	11	12	For further details, see footnote "c" at the end of the table.
Hexosaminidase enzyme activity	X	X													Only for primary population. Samples will be collected for all participants during screening or at D1 (predose). Only 1 sample will be collected, during screening or at D1 after 4 hr fasting. For those with historical results, they may begin the study without
Lumbar puncture	X ^d								X ^e						
^d LP will be performed once participant demonstrates eligibility based on screening criteria. The LP may be done during the screening period within 14 days prior to treatment initiation (D -14 to D -1). The LP should be done successfully before first dose and/or randomization.
 
^e The LP should be done after all other assessments if possible.

Study Period/ Procedure	Screening	Primary analysis treatment period								Open-label extension treatment period				FU Period	Notes
Day or Week	Up to 60 d before D1	W1/D1	W12 (±7d)	W26 (±7d)	W39 (±7d)	W52 (±7d)	W65 (±7d)	W78 (±7d)	W104 (±7d)/EW ^a	W130 (±14d)	W156 (±14d)	W182 (±14d)	W208 (±14d)/EOT/EW ^b	W214 (±7d) SFU after EOT	
Visit number	1	2	3	4	4.1 ^c	5	5.1 ^c	6	7	8	9	10	11	12	For further details, see footnote "c" at the end of the table.
Study IMP administration															
Randomization		X													For the primary population only.
IRT contact	X	X	X	X	X	X	X	X	X	X	X	X	X	X	For Canadian participants enrolled in the US, see Section 10.8 .
Dispense IMP		X	X	X	X	X	X	X	X	X	X	X			In addition to the IMP dispensing at these clinical site visits, IMP will be dispensed at remote site visits where applicable via DTP shipment. At Visit 4.1 (W39) and Visit 5.1(W65), IMP will be dispensed and sent to participants via DTP shipment. For Canadian participants enrolled in the US, see Section 10.8 .

Study Period/ Procedure	Screening	Primary analysis treatment period								Open-label extension treatment period				FU Period	Notes
Day or Week	Up to 60 d before D1	W1/D1	W12 (±7d)	W26 (±7d)	W39 (±7d)	W52 (±7d)	W65 (±7d)	W78 (±7d)	W104 (±7d)/EW ^a	W130 (±14d)	W156 (±14d)	W182 (±14d)	W208 (±14d)/EOT/EW ^b	W214 (±7d) SFU after EOT	
Visit number	1	2	3	4	4.1 ^c	5	5.1 ^c	6	7	8	9	10	11	12	For further details, see footnote "c" at the end of the table.
Venglustat or placebo		←----- Once daily ----->													Participants in the primary population will receive venglustat or placebo once daily for 104 weeks in a double-blind manner in the primary analysis period and receive venglustat once daily for 104 weeks in an open-label manner in the open-label extension period. Participants in the secondary population will receive venglustat for 208 weeks in an open-label manner. Participants will take the first IMP dose of open-label extension period dispensed at Visit 7 on the day after completion all Visit 7 assessments.
Dispense /Check/Retrieve Patient Diary	X ^f	X	X	X		X		X	X	X	X	X	X	X ^g	f dispense only g retrieve only
Telephone call to participants		←----->													Telephone call follow-ups to occur every 60 ±3 days after D 1, except for scheduled follow up phone calls which would fall within a few days (up to 10 days) from a site visit. Assessments include participant status, AEs, participant diary, IMP compliance, and concomitant medications. For participants who withdraw early from the treatment, follow-up telephone call should occur up to 6 weeks after last dose of study IMP. An unscheduled

Study Period/ Procedure	Screening	Primary analysis treatment period								Open-label extension treatment period				FU Period	Notes
Day or Week	Up to 60 d before D1	W1/D1	W12 (±7d)	W26 (±7d)	W39 (±7d)	W52 (±7d)	W65 (±7d)	W78 (±7d)	W104 (±7d)/EW ^a	W130 (±14d)	W156 (±14d)	W182 (±14d)	W208 (±14d)/EOT/EW ^b	W214 (±7d) SFU after EOT	
Visit number	1	2	3	4	4.1 ^c	5	5.1 ^c	6	7	8	9	10	11	12	
															phone visit or a remote monitoring may be required due to regional or national emergency as declared by a governmental agency.
Physical examination	X ^h	X ^h	X ^h	X ^h		X ^h		X ^h	X ^h	X ^h	X ^h	X ^h	X ^h	X ⁱ	^h complete/full physical examination including visual acuity. ⁱ abbreviated/brief physical examination.
Neurological examination	X								X		X		X		When neurological and ophthalmological examinations are performed on the same day, the neurological examination should be performed before the ophthalmological examination.
Body weight	X	X	X	X		X		X	X	X	X	X	X	X	
Height	X	X ^j	X ^j	X ^j		X ^j		X ^j	X ^j	X ^j	X ^j	X ^j	X ^j		^j For juvenile and adolescent participants only.
Archival blood sample		X													This sample will be collected and stored for use if any unexpected safety issue occurs to ensure that a predose baseline value is available for previously nonassessed parameters.
Vital signs	X	X	X	X		X		X	X	X	X	X	X	X	Includes heart rate, systolic and diastolic blood pressure, respiratory rate, and body temperature.
Serum β-hCG	X														

Study Period/ Procedure	Screening	Primary analysis treatment period								Open-label extension treatment period				FU Period	Notes
Day or Week	Up to 60 d before D1	W1/D1	W12 (±7d)	W26 (±7d)	W39 (±7d)	W52 (±7d)	W65 (±7d)	W78 (±7d)	W104 (±7d)/EW ^a	W130 (±14d)	W156 (±14d)	W182 (±14d)	W208 (±14d)/EOT/EW ^b	W214 (±7d) SFU after EOT	
Visit number	1	2	3	4	4.1 ^c	5	5.1 ^c	6	7	8	9	10	11	12	For further details, see footnote "c" at the end of the table.
pregnancy test (for WOCBP)															
Urine pregnancy test (for WOCBP)		←-----Every 4 weeks-----→												Female patients of childbearing potential only. Results will be captured in patient diary when test is not taken at the clinic. At V2, it must be negative before the first IMP administration.	
Serology tests for hepatitis B, C, and other infectious disease, if locally required	X														
Hematology, biochemistry, urinalysis	X	X	X	X		X		X	X	X	X	X	X	X	Urinalysis by dipstick will be performed at the site. If abnormal, a complete urinalysis will be performed by the central laboratory
Urine biochemistry (including UPCR and UACR) ^k		X	X	X		X		X	X	X	X	X	X		

Study Period/ Procedure	Screening	Primary analysis treatment period								Open-label extension treatment period				FU Period	Notes
Day or Week	Up to 60 d before D1	W1/D1	W12 (±7d)	W26 (±7d)	W39 (±7d)	W52 (±7d)	W65 (±7d)	W78 (±7d)	W104 (±7d)/EW ^a	W130 (±14d)	W156 (±14d)	W182 (±14d)	W208 (±14d)/EOT/EW ^b	W214 (±7d) SFU after EOT	
Visit number	1	2	3	4	4.1 ^c	5	5.1 ^c	6	7	8	9	10	11	12	For further details, see footnote “c” at the end of the table.
															^k First morning void urine sample to be collected on the day of the site visit or home visit (where allowed per local regulations). Second morning void urine sample can be collected if first morning void urine sample was not collected. Courier transportation can be arranged as required and if allowed per local regulations. Urine sample should be sent to the central laboratory for quantitative measurement of creatinine, total protein and albumin which will be used to calculate the urine albumin/creatinine ratio and urine protein/creatinine ratio.
12-lead ECG	X	X ^l		X		X		X	X		X		X		^l ECG in triplicate will be performed prior to IMP administration. Please note that ECG is required in triplicate only at Visit 2.
Ophthalmological examination	X ^m			X ⁿ		X ⁿ		X ⁿ	X ^m	X ^o	X ^o	X ^o	X ^m		^m Full ophthalmological examination (including slit lamp fundoscopy with dilation), photography, and ARLNS for all participants.

Study Period/ Procedure	Screening	Primary analysis treatment period								Open-label extension treatment period				FU Period	Notes
Day or Week	Up to 60 d before D1	W1/D1	W12 (±7d)	W26 (±7d)	W39 (±7d)	W52 (±7d)	W65 (±7d)	W78 (±7d)	W104 (±7d)/EW ^a	W130 (±14d)	W156 (±14d)	W182 (±14d)	W208 (±14d)/EOT/EW ^b	W214 (±7d) SFU after EOT	
Visit number	1	2	3	4	4.1 ^c	5	5.1 ^c	6	7	8	9	10	11	12	For further details, see footnote "c" at the end of the table.
															
n Full ophthalmological examination (including slit lamp funduscopy with dilation) for all participants.
 
o Full ophthalmological examination (including slit lamp funduscopy with dilation), for participants ≥2 and <18 years of age only.
 
Full ophthalmological examination, photography, and ARLNS can be performed at any time if deemed medically necessary. When neurological and ophthalmological examinations are performed on the same day, the neurological examination should be performed before the ophthalmological examination.

AE collection	X	X	X	X		X		X	X	X	X	X	X	X	AEs will be captured from the time the participant provides signed informed consent through the safety follow-up period up to 6 weeks after the W208 EOT visit.
Prior and concomitant medications	X	X	X	X		X		X	X	X	X	X	X	X	

Study Period/ Procedure	Screening	Primary analysis treatment period								Open-label extension treatment period				FU Period	Notes
Day or Week	Up to 60 d before D1	W1/D1	W12 (±7d)	W26 (±7d)	W39 (±7d)	W52 (±7d)	W65 (±7d)	W78 (±7d)	W104 (±7d)/ EW ^a	W130 (±14d)	W156 (±14d)	W182 (±14d)	W208 (±14d)/ EOT/EW ^b	W214 (±7d) SFU after EOT	W1/D1 visit will be Baseline visit. For further details, see footnotes “a” and “b” at end of the table.
Visit number	1	2	3	4	4.1 ^c	5	5.1 ^c	6	7	8	9	10	11	12	For further details, see footnote
Pharmacokinetics															
Plasma samples		X ^r	X ^s	X ^t		X ^t			X ^u						^r For primary population, sampling will be performed predose and 0.5, 3, 8, 12, and 24 hours postdose in 15 participants (Plasma sample ID P00, P01, P02, P03, P04, P05, respectively). This PK profile sub study will stop when required numbers of samplings are collected. For all other participants, sampling will be performed only at 3 hours postdose (P02). Participants will receive IMP at clinical site on this day.

Study Period/ Procedure	Screening	Primary analysis treatment period								Open-label extension treatment period				FU Period	Notes
Day or Week	Up to 60 d before D1	W1/D1	W12 (±7d)	W26 (±7d)	W39 (±7d)	W52 (±7d)	W65 (±7d)	W78 (±7d)	W104 (±7d)/EW ^a	W130 (±14d)	W156 (±14d)	W182 (±14d)	W208 (±14d)/EOT/EW ^b	W214 (±7d) SFU after EOT	
Visit number	1	2	3	4	4.1 ^c	5	5.1 ^c	6	7	8	9	10	11	12	For further details, see footnote "c" at the end of the table.
															
s Sampling will be performed predose and 0.5, 3, 8, 12, and 24 hours postdose (Plasma sample ID P06, P07, P08, P09, P10, P11 respectively).
 
t Sampling will be performed predose and 3 hours postdose. (Plasma sample ID P12, P13 at Visit 4/Week 26 and P14 and P15 at Visit 5/Week 52, respectively). Participants will receive IMP at the clinical site on these days.
 
u Sampling will be performed predose (plasma sample ID P16 for participants who complete the V7/W104 visit; plasma sample ID P18 for participants who complete the EW visit.)

CSF samples									X ^v						v Sampling will be performed predose (CSF sample ID C00).
Assessments															
9-HPT	X	X	X	X		X		X	X		X		X		
Timed 25-FWT	X	X	X	X		X		X	X		X		X		
FARS Part I, functional staging of ataxia	X	X	X	X		X		X	X		X		X		
FARS Part II, Activities of Daily	X	X	X	X		X		X	X		X		X		

Study Period/ Procedure	Screening	Primary analysis treatment period								Open-label extension treatment period				FU Period	Notes
Day or Week	Up to 60 d before D1	W1/D1	W12 (±7d)	W26 (±7d)	W39 (±7d)	W52 (±7d)	W65 (±7d)	W78 (±7d)	W104 (±7d)/EW ^a	W130 (±14d)	W156 (±14d)	W182 (±14d)	W208 (±14d)/EOT/EW ^b	W214 (±7d) SFU after EOT	
Visit number	1	2	3	4	4.1 ^c	5	5.1 ^c	6	7	8	9	10	11	12	For further details, see footnote "c" at the end of the table.
Living															
FARS Part III, neurological examination	X	X	X	X		X		X	X		X		X		
Muscle weakness of triceps and quadriceps		X	X	X		X		X	X		X		X		
FARS functional test, PATA	X	X	X	X		X		X	X		X		X		

Study Period/ Procedure	Screening	Primary analysis treatment period								Open-label extension treatment period				FU Period	Notes
Day or Week	Up to 60 d before D1	W1/D1	W12 (±7d)	W26 (±7d)	W39 (±7d)	W52 (±7d)	W65 (±7d)	W78 (±7d)	W104 (±7d)/EW ^a	W130 (±14d)	W156 (±14d)	W182 (±14d)	W208 (±14d)/EOT/EW ^b	W214 (±7d) SFU after EOT	W1/D1 visit will be Baseline visit. For further details, see footnotes "a" and "b" at end of the table.
Visit number	1	2	3	4	4.1 ^c	5	5.1 ^c	6	7	8	9	10	11	12	For further details, see footnote "c" at the end of the table.

Abbreviations: 9-HPT, 9-hole peg test; ADL, activities of daily living, a PRO from the FARS; ADME, absorption, distribution, metabolism, excretion; [REDACTED]; AE, adverse event; ARLNS, Age-Related Eye Disease Study (AREDS) Clinical Lens Grading System; β-hCG, beta human chorionic gonadotropin; [REDACTED]; CSF, cerebrospinal fluid; d, days; D, day; DTP, direct to patient; ECG, electrocardiogram; EOT, end of treatment; EW, early withdrawal; FARS, Friedreich's Ataxia Rating Scale; FU, follow-up; HBV, hepatitis B; HCV, hepatitis C; HIV, human immunodeficiency virus; IMP, investigational medicinal product; IRT, interactive response technology; LP, lumbar puncture; [REDACTED]; [REDACTED] NIH, National Institutes of Health; NTSAD, National Tay-Sachs & Allied Diseases Associations; [REDACTED] PATA, a speech test using the phrase "pata"; [REDACTED] PK, pharmacokinetic; [REDACTED]; [REDACTED]; W, week; WOCBP, woman of childbearing potential.

Note: All screening assessments are not required to be repeated for participant rescreening. Cognitive, behavioral, and ataxia assessments are not required to be repeated if performed within 3 months.

Note: [REDACTED] questionnaires should be completed by the participants before the consultation and/or clinical tests.

- a In case of early treatment withdrawal before W104, and if participant does not wish to stay in the study, assessments mentioned in the W104 visit will be performed, followed by safety follow-up visit 6 weeks after the W104/EW visit.
- b In case of early treatment withdrawal after W104, and if participant does not wish to stay in the study after W104, assessments mentioned in the W208 will be performed, followed by safety follow-up visit 6 weeks after the W208/EOT/EW visit.
- c The IMP can be dispensed and sent to participants at Visits 4.1 (W39) and 5.1 (W65) via DTP shipment except if the local regulatory authority requires the IMP dispensed at site. No other study assessments are planned during these 2 visits.

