During the time of the review of this risk on 15th August 2022, there were 13 participants aged 2 to <18 years enrolled in the AMETHIST study, 8 of whom were aged 2 to <12, and no lens opacity or cataracts have been observed in these participants. However, there is the potential for venglustat-related lenticular degeneration based on results from the juvenile rat toxicity study. Due to limited pediatric data in children from 2 to <18 years old, there still is a potential for venglustat-mediated lenticular degeneration and therefore children are potentially at greater risk than adults (EM = 3.7), given that juvenile female rat NOAEL exposure is less than therapeutic (ie, EM = 0.6). Importantly, a cataract that develops during childhood before the age of 8 to 10 year can lead to irreversible severe sequelae including blindness. The outcome of cataract surgery for younger participants is not as successful as for adults. Therefore, the potential risk of new or worsening lens opacity cannot be excluded in children 2 to less than 18 years old. Close ophthalmology monitoring of this population, if included in venglustat studies, will therefore be maintained. Children <2 years of age are excluded in the venglustat development program.

If a participant develops signs or symptoms concerning for cataract development or other visual problems at any time during the study, the Investigator may refer the participant to a specialist for a comprehensive ophthalmological examination as a part of participant's medical care.

Potential male infertility due to exposure in childhood (<12 years of age)

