2.3.1.6 Embryo-fetal toxicity

The important potential risk of embryo-fetal toxicity is based on the non-clinical findings in rats and rabbits such as increased implantation loss (in rats) and reduced fetal weight (in both rats and rabbits). In the pre-/postnatal development toxicity study in rats, increased unaccounted-for sites (implantation sites without a corresponding pup), decreased mean numbers of pups born and decreased mean pup weight were observed. There have been no studies of venglustat in pregnant women.

Pregnant women should not receive venglustat, thus contraception measures are part of the protocol ([Section 5.1](#) and [Section 10.4](#)).

Table 2 - Risk mitigation strategy

Description	Summary of data/rationale	Mitigation strategy
Potential risks (venglustat)		
New or worsening lens opacity in children two to less than 18 years old (important potential risk)	Based on the review of the available clinical data, and the development of human eye, this is no longer considered as potential risk in adult populations. In the absence of clinical pediatric data in children two-years to <18 years of age, children are potentially at risk for venglustat. Importantly, cataract that develops during childhood before the age of eight to 10 year can lead to irreversible severe sequelae including blindness.	For pediatric population: comprehensive ophthalmological examination and periodic monitoring. If a participant develops signs or symptoms concerning for cataract development or other visual problems at any time during the study, comprehensive ophthalmological examination will be performed.
Potential male infertility due to exposure in childhood (<12 years of age) (important potential risk)	Preclinical findings (rat). See IB Section 7.1.	Individual benefit-risk assessment by the Investigator and patients/parents/guardians.
Depression Adverse neurological and psychiatric events are being monitored in all venglustat studies given the compound's access to the central nervous system.	Ability of venglustat to cross the blood-brain barrier. See IB Section 7.1.	Neurological examinations Depression is considered as a treatment monitored event in all ongoing and upcoming venglustat clinical programs.

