8.2.1 Physical examinations

- A complete/full physical examination will include, at a minimum, assessments of the general appearance, examination of the skin; head, eyes (including visual acuity), ears, nose, and throat; lymph nodes; heart, lungs, and abdomen; extremities and joints; and neurological and mental status. Height and weight will also be measured and recorded.
- An abbreviated/brief physical examination will include, at a minimum, general assessments.
- Investigators should pay special attention to clinical signs related to previous serious illnesses.
- Any new finding or worsening of previous finding should be reported as a new AE.

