3.6 SAFETY ANALYSES

All safety analyses will be performed on the safety populations as defined in [Section 2](#) for the two steps analysis, unless otherwise specified, using the following common rules:

- The analysis of the safety variables will be essentially descriptive, and no testing is planned.
- Safety data in participants who do not belong to the safety population (eg, exposed but not randomized) will be provided separately if any.

In the first step analysis, safety data will be presented for the following period:

- Safety analysis of the primary analysis period. This analysis will present safety data collected during the primary analysis period (as defined in [Section 3.1](#)). Safety analyses will present safety data in the following arms:
 - Primary population – Placebo: participants from the primary population, having received placebo during the primary analysis period.
 - Primary population – Venglustat: participants from the primary population, having received venglustat during the primary analysis period.
 - Secondary population – Venglustat: participants from the secondary population, having received venglustat during the primary analysis period.

In the second step analysis, safety data will be presented separately for the two following periods:

- Safety analysis of the OLE period. This analysis will present safety data collected during the OLE period (as defined in [Section 3.1](#)). Only participants having received venglustat during the OLE period will be included in this analysis. Safety analyses will present safety data from the following groups:
 - Primary population - Delayed venglustat: participants from the primary population, having received placebo during the primary analysis period, then having received venglustat during the OLE period.
 - Primary population - Early venglustat: participants from the primary population, having received venglustat during the primary analysis period, then having continued to receive venglustat during the OLE period.

- Primary population - All venglustat: all participants from the primary population having received venglustat during the OLE period.
- Secondary population – Venglustat: participants from the secondary population having received venglustat during the OLE period.

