3.6.3 Additional safety assessments

3.6.3.1 *Laboratory variables, vital signs and electrocardiograms (ECGs)*

The following laboratory variables, vital signs and electrocardiogram (ECG) variables will be analyzed. They will be converted into standard international units.

- Hematology:
 - Red blood cells and platelets and coagulation: hemoglobin, hematocrit, erythrocyte count, platelet count.
 - White blood cells: white blood cell count, neutrophils, lymphocytes, monocytes, basophils, eosinophils.
- Clinical chemistry:
 - Metabolism: glucose, protein.
 - Electrolytes: sodium, potassium.
 - Renal function: creatinine, blood urea nitrogen, estimated Glomerular Filtration Rate (eGFR).
 - Liver function: alanine aminotransferase, aspartate aminotransferase, alkaline phosphatase, total and direct bilirubin.
 - Pregnancy test: Serum β -human chorionic gonadotropin (all female participants).
- Urinalysis:
 - Urinalysis for quantitative analysis: pH, proteins, and glucose.

- Vital signs: heart rate, systolic and diastolic blood pressure, weight.
 - For all Blood Pressure (BP) and Heart Rate (HR) measurements, will be analyzed using the supine measurements at each visit.
- ECG variables: heart rate, PR, QRS, QT, and corrected QTc (according to Bazett/Fridericia).

For ECG at baseline visit (V2) a triplicate of data is collected. For calculation of baseline value, the average of all available data will be calculated.

eGFR will be derived using the Chronic Kidney Disease Epidemiology Collaboration (CKD-EPI) creatinine equation for adult participants and the Schwartz formula for pediatric participants.

Quantitative analyses

For all laboratory variables, vital signs and ECG variables above, descriptive statistics for results and changes from baseline will be provided for each visit, the last value and the worst value (minimum and/or maximum value depending on the parameter) during the on-treatment period.

All laboratory parameters and vital signs parameters will be summarized using the analysis windows as defined in [Section 5.4, Table 13](#) and into account planned visit in the protocol.

When appropriate, plots of mean \pm SE over time will be presented. Plots of mean change from baseline \pm SE will also be presented.

Analyses according to PCSA

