5.3 APPENDIX 3 DEMOGRAPHICS AND BASELINE CHARACTERISTICS, PRIOR OR CONCOMITANT MEDICATIONS

The following demographics and baseline characteristics, medical and surgical history and disease characteristics will be summarized using descriptive statistics in the randomized population.

Demographic and baseline characteristics

- Gender (Male, Female).
- Age in years (quantitative and categorical variable: Children (2-11 years), Adolescents (12-17 years), 18 to <65, 65 to <85 and ≥85 years), the two first categories are applicable only to participants in the secondary population.
- Race (White, Black or African American, Asian, American Indian or Alaska Native, Native Hawaiian or other Pacific Island, other).
- Ethnicity (Hispanic, non-Hispanic).
- Weight in kilograms (quantitative and categorical variable: 10 to <15, 15 to <30, 30 to <50, 50 to <100, ≥100).
- Body mass index (BMI) in kg/m² (quantitative and categorical variable: <18.5, 18.5 to <25, 25 to <30, ≥30).

Randomization strata

The randomization strata is only applicable for primary population. The two categories will be presented: able to walk, unable to walk.

Disease characteristics

The time since diagnosis and time since symptom onset will be derived from the subtraction between two years: year of randomization and year of diagnosis or symptom onset. A value of zero means that diagnosis or symptom were occurred the year of randomization.

Based on the same principle, the age at diagnosis and age at symptom onset will be derived from the difference between the year of diagnosis or symptom onset and the year of birth.

Medical or surgical history

Medical (or surgical) history includes previous relevant medical and surgery history collected at baseline. Medical and surgical history will be coded to a LLT, PT, HLT, HLGT, and associated to

a primary SOC using the MedDRA version currently in effect at Sanofi at the time of database lock.

Medical/ surgical history will be summarized in each treatment arm by primary SOC and PT. Events will be sorted by SOC internationally agreed order and decreasing frequency of PT based on the incidence in the primary population.

Alcohol habits at baseline

Alcohol habits include:

- Frequency of alcoholic drinks in the last 12 months (Never/Occasional/At least monthly/At least weekly/At least daily).

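### Serial height in children is not analysed, and raw weight change in one pooled arm cannot distinguish normal from slowed growth

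*Protocol*

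**What the plan says.** **Collection.** In protocol 1.3, Table 1, the screening height carries no footnote and so applies to everyone. The ten later heights (Day 1 and Weeks 12, 26, 52, 78, 104, 130, 156, 182 and 208) carry the note "For juvenile and adolescent participants only". Body weight is taken at all of these visits. Protocol 8.2.1 says of the full physical examination that "Height and weight will also be measured and recorded", with no age limit.

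**Analysis.** The readable list in SAP 3.6.3.1 gives "Vital signs: heart rate, systolic and diastolic blood pressure, weight". Height is not on it. For the listed variables, "descriptive statistics for results and changes from baseline will be provided for each visit". No standardised score, percentile or growth velocity is mentioned.

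**Arms.** SAP 3.6 reports children in one secondary-population arm, defined as "participants from the secondary population, having received venglustat during the primary analysis period", with a matching single arm for the open-label extension. Neither is split by age. Inclusion criterion I 01 (protocol 5.1) allows adults in the secondary population as well as participants from 2 years.

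**Other uses of height.** SAP 5.3 lists "Body mass index (BMI) in kg/m"² as a baseline characteristic, and SAP 5.4 gives its formula. SAP 3.6.3.1 also names the Schwartz formula for paediatric eGFR without writing it out.

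**The concern.** Repeated height in children and adolescents alone looks like a deliberate paediatric measurement, yet no readable part of the SAP turns it into a result. That leaves raw weight change to carry any information on growth. In an adult, zero is a natural reference for weight change. In a child it is not: the expected change is positive and depends on age and sex. A child growing well below expectation still shows a gain.

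The secondary population is planned to receive venglustat for 208 weeks, with no paediatric control arm for comparison. A table showing a mean weight gain in this arm could be read as reassuring when it carries almost no information on whether the children grew as expected.

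**Working it through.** The plan gives no figure of its own to reproduce here. The check has two parts: tracing the variables through the documents, and an illustration of what the planned weight summary would show.

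**Trace**

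| Item | Collected | Planned output |
|---|---|---|
| Height, under 18 | Screening plus ten visits | None by visit; feeds baseline BMI and, if the eGFR formula uses height (my assumption, since the SAP does not write it out), eGFR |
| Weight, all | Same visits, plus safety follow-up | Value and change from baseline by visit, one pooled secondary arm; abnormality (PCSA) incidence |
| Age group | Known at enrolment | Demographic categories; age-dependent PCSA definitions; paediatric subsets for acceptability and for extension-period eye results; no split of weight |

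**Illustration: inputs**
- Children in the arm: protocol 2.3.1.1 says that at the August 2022 risk review "there were 13 participants aged 2 to <18 years enrolled in the AMETHIST study".
- Arm size: up to 20 (protocol 1.1 and 4.1). If that cap held, the children's share *p* at enrolment is at least 13/20 = 0.65. The documents do not say how many adults enrolled, so *p* could be as high as 1.0.
- Expected gain *g*: assumed 2 to 5 kg a year in children and 0 in adults. These are assumptions, not document figures.
- Slowing *s*: 0 (normal), 0.25 or 0.5 of the expected gain lost.

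**Formula:** arm mean weight change at Week 104 = p × g × 2 years × (1 − s)

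| g (kg/year) | p | s = 0 | s = 0.25 | s = 0.5 |
|---|---|---|---|---|
| 2 | 0.65 | +2.6 | +1.95 | +1.3 |
| 2 | 1.0 | +4.0 | +3.0 | +2.0 |
| 3 | 0.65 | +3.9 | +2.93 | +1.95 |
| 3 | 1.0 | +6.0 | +4.5 | +3.0 |
| 5 | 0.65 | +6.5 | +4.88 | +3.25 |
| 5 | 1.0 | +10.0 | +7.5 | +5.0 |

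Normal growth gives +2.6 to +10.0 kg and growth at half speed gives +1.3 to +5.0 kg. Every value is a gain, and the two ranges overlap from +2.6 to +5.0 kg.

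**Same number, different growth**
1. Different share of adults: 0.65 × 3 × 2 × 1 = 3.9 kg (65% children, normal growth), and 1.0 × 3 × 2 × 0.65 = 3.9 kg (all children, growth slowed by 35%). The age categories in SAP 5.3 would show the share, so a reader could partly resolve this case.
2. Same share of adults: 0.65 × 2 × 2 × 1 = 2.6 kg (expected 2 kg a year, normal growth), and 0.65 × 4 × 2 × 0.5 = 2.6 kg (expected 4 kg a year, half speed). Knowing the share does not resolve this one; only a scale that accounts for each child's age and sex does.

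The second case shows that taking the adults out is not enough on its own.

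**The case against.** The strongest case on the other side has five parts.

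- **Other routes exist.** Weight is among the variables screened for PCSA (SAP 3.6.3.1), and in children those definitions depend on age category (SAP 5.4). New or worse examination findings are reported as adverse events (protocol 8.2.1), and an independent committee monitors safety. This stands in part. A reader might infer that slowed growth could never come to light; the documents do not support that. But the PCSA criteria are a sponsor list that is not in the documents. A criterion based on weight loss would not fire for a child who gains too slowly, and height is not a listed variable.
- **There is no animal signal for growth in dosed young.** A reader might lean on protocol 2.3.1.6, where "decreased mean numbers of pups born and decreased mean pup weight were observed". That comes from pre-/postnatal exposure and is listed under embryo-fetal toxicity. The juvenile rat studies summarised in 2.3.1.1 lead to lens and testicular risks, not to a growth effect. This objection stands, and the point does not rest on the pup-weight finding.
- **No commitment is broken.** Growth is not a named risk in protocol 2.3.1 or a named endpoint in the readable text. This stands.
- **The mix of ages is not established.** Adults are allowed in the arm but their number is not given. This stands, which is why the illustration runs up to an all-child arm; the problem remains there.
- **Redaction.** The exploratory objectives are blacked out, so a growth measure there cannot be excluded. The safety list in SAP 3.6.3.1 is readable and omits height.

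**Conclusion.** The point holds as a weakness in the prespecified safety reporting. Height repeated at ten visits in children has no planned by-visit result in the readable SAP. The planned weight summary cannot separate normal from slowed growth, because it is unstandardised and pools ages from 2 years upward, possibly with adults.

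That conclusion needs only one premise: children are expected to gain weight, by an amount that varies with age. The kilogram figures are illustrations under assumed gains and should not be quoted as expected results.

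Two stronger readings are not supported. The documents give no evidence that venglustat slows growth. Nor is the information lost: individual heights and weights are recorded, so standardised scores could be derived later, though no longer as a prespecified output. The primary and secondary efficacy conclusions are unaffected. The change is still worth making before database lock. The SAP already treats children separately for eye results, acceptability and PCSA definitions, and plans individual plots for secondary-population biomarkers and efficacy, so growth data would fit its existing approach.

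**What to change.** In SAP 3.6.3.1, for participants under 18 years at enrolment:

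- add height to the analysed variables;
- report height and weight at each visit as age- and sex-standardised SD scores, with change from baseline and individual plots, in both analysis steps;
- name the growth reference;
- show weight separately for children and adults, keeping raw change as the adult summary.

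State how age at each visit is derived. SAP 5.4 counts age during the study from randomisation, but these participants are not randomised; its Day 1 rule, which uses first dose, would serve.

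Separately, reconcile protocol 8.2.1, which puts height in every full examination without an age limit, with the Schedule of Activities, which limits it to juvenile and adolescent participants after screening.

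**Cost:** SAP text and programming; age, sex, height and weight are already collected. **Limits:** numbers are small, and height may be hard to measure in non-ambulant children. With no paediatric control, the scores show departure from reference growth but cannot separate a drug effect from the underlying diseases.
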